## 5.8 General Concomitant Medication and Supportive Care Guidelines

All supportive therapy for optimal medical care will be given during the study period at the discretion of the attending physician(s) within the parameters of the protocol and documented on source documents as concomitant medication.

Concurrent or concomitant use of medication is not restricted during protocol therapy. However, patients are not permitted to take any anti-cancer medications or supplements during study duration.

Few side effects of ATB have been reported. ATB has shown to improve many baseline gastrointestinal symptoms particularly those associated with GERD. However, diarrhea has been rarely reported in relation to ATB administration and should be managed using the following guidelines.

- Loperamide (Imodium®)

All patients should be instructed to begin taking loperamide at the earliest signs of diarrhea and/or abdominal cramping that occur more than eight hours after receiving ATB. Patients will be instructed to begin taking loperamide at the earliest signs of (1) a poorly formed or loose stool, (2) the occurrence of one to two more bowel movements than usual in one day, or (3) unusually high volume of stool. Loperamide should be taken in the following manner: 4 mg at the first onset of diarrhea, then 2 mg every two hours around the clock until diarrhea-free for at least 12 hours. Patients may take 4 mg of loperamide every four hours during the night. Additional antidiarrheal measures may be used at the discretion of the treating physician.

## 5.9 Dietary Restrictions

No food interactions are known to occur with ATB, thus, no dietary restrictions will be placed upon participants

## 5.10 Monitoring Subject Compliance

ATB will be administered or dispensed only to eligible patients under the supervision of the investigator or trained study staff or identified sub investigator(s). The appropriate study personnel will maintain records of study agent receipt and dispensing. Comprehensive instructions will be provided to the patient to ensure compliance with dosing procedures.

## 6 ADVERSE EVENTS: DEFINITIONS, COLLECTION, REPORTING REQUIREMENTS AND SAFETY ASSESSMENT

### 6.1 Definitions

#### 6.1.1 Adverse Event

Any untoward medical occurrence in a patient or clinical investigation subject administered a pharmaceutical product and which does not necessarily have to have a causal relationship with this treatment. (International Conference on Harmonisation [ICH], E2A, E6).

This study will utilize the NCI Common Terminology Criteria for Adverse Events (CTCAE) version 5.0, located on the CTEP web site:

[https://ctep.cancer.gov/protocolDevelopment/electronic\\_applications/ctc.htm](https://ctep.cancer.gov/protocolDevelopment/electronic_applications/ctc.htm)

AEs may be spontaneously reported by the patient and/or in response to an open question from study personnel or revealed by observation, physical examination or other diagnostic procedures.

#### 6.1.2 Serious Adverse Event (SAE)

Serious Adverse Event (SAE) means any untoward medical occurrence that results in any of the following outcomes:

- **Death.** Results in death.
- **Life threatening.** Is life threatening (refers to an AE in which the patient was at risk of death at the time of the event. It does not refer to an event which hypothetically might have caused death if it were more severe).
- **Hospitalization.** Requires inpatient hospitalization or prolongation of an existing hospitalization (see clarification in the paragraph below on planned hospitalizations).
- **Disability/incapacity.** Results in persistent or significant disability or incapacity. (Disability is defined as a substantial disruption of a person's ability to conduct normal life functions).
- **Pregnancy.**
- **Medically important event.** This refers to an AE that may not result in death, be immediately life threatening, or require hospitalization, but may be considered serious when, based on appropriate medical judgment, may jeopardize the patient, require medical or surgical intervention to prevent one of the outcomes listed above, or involves suspected transmission via a medicinal product of an infectious agent. Examples of such medical events include allergic bronchospasm requiring intensive treatment in an emergency room or at home, blood dyscrasias or convulsions that do not result in inpatient hospitalization, or the development of drug dependency or drug abuse; any organism, virus, or infectious particle (e.g., prion protein transmitting transmissible spongiform encephalopathy), pathogenic or nonpathogenic, is considered an infectious agent.

### 6.1.3 Attribution of an Adverse Event

An assessment of the relationship between the adverse event and the medical intervention, using the following categories:

**Definitely Related:** *The AE is clearly related to the intervention.* There is clear evidence to suggest a causal relationship, and other possible contributing factors can be ruled out.

**Probably Related:** *The AE is likely related to the intervention.* There is evidence to suggest a causal relationship, and the influence of other factors is unlikely.

**Possibly Related:** *The AE may be related to the intervention.* There is some evidence to suggest a causal relationship (e.g., the event occurred within a reasonable time after administration of the trial medication). However, the influence of other factors may have contributed to the event (e.g., the subject's clinical condition, other concomitant events).

**Unlikely:** *The AE is doubtfully related to the intervention.* A clinical event, including an abnormal laboratory test result, whose temporal relationship to drug administration makes a causal relationship improbable (e.g., the event did not occur within a reasonable time after administration of the trial medication) and in which other drugs or chemicals or underlying disease provides plausible explanations (e.g., the subject's clinical condition, other concomitant treatments).

**Unrelated:** *The AE is clearly NOT related to the intervention.* The AE is completely independent of study drug administration, and/or evidence exists that the event is definitely related to another etiology.

### 6.1.4 Expectedness of an Adverse Event

Study investigator or treating physician will be responsible for determining whether an AE is expected or unexpected as indicated in the protocol, informed consent form and/or drug information brochure. An AE will be considered unexpected if the nature, severity, or frequency of the event is NOT consistent with the risk information previously described for the study intervention.

## 6.2 Collection and Reporting Requirements for Adverse Events and Serious Adverse Events

### 6.2.1 Collection of Adverse Events

All (or specify if only certain grade AE needed) adverse events (including SAEs) must be recorded in OnCore® and/or an adverse event log. All AEs required to be collected must be graded according to the CTCAE v5. When possible, signs and symptoms indicating a common underlying pathology should be noted as one comprehensive event. Investigator's or treating physician's assessment of AE attributions must also be documented.

AEs will be collected from the time the subject signs the consent form through 30 days post last dose of study drug(s). AEs will be tracked and followed until resolution, subject withdraws consent, or is lost to follow-up (including subjects who discontinue early). All adverse events collected per the protocol will be followed with appropriate medical management until they are resolved, if they are related to the study treatment, or until the investigator deems the event to be chronic.

Please see section 6.2.2 and table 4 to identify the adverse events that need to be reported.

## 6.2.2 Reporting of Adverse Events and Serious Adverse Events

Please refer to table 4 below to identify adverse events that meet reporting requirements.

All serious adverse events (SAEs) that occur after the subject has signed the consent form through 30 days post last dose of study drug(s) will be reported. All SAEs will be followed until satisfactory resolution, or until the investigator deems the event to be chronic.

All serious adverse events (SAEs) must also be documented in OnCore®.

**Table 4**

Attribution	SAE				AE		
	Grade 1, 2 & 3		Grade 4 and 5		Grade 3	Grade 4	
	Expected	Unexpected	Expected	Unexpected	Unexpected	Expected	Unexpected
Unrelated Unlikely	IRB  and DSMC  - Routine Review 	IRB  and DSMC  - Routine Review 	IRB  - Routine Review 	IRB  - Routine Review 	DSMC  - Routine Review 	DSMC  - Within 5 calendar days	DSMC  - Within 5 calendar days
Possible Probable Definite		IRB  and DSMC  - Within 5 calendar days	DSMC  - Within 5 calendar days	IRB  and DSMC  - Within 5 calendar days			

1. Guidance on adverse event reporting to the IRB is available online at MCW IRB Policies and Procedures.
2. For expedited DSMC reporting, study coordinator/research nurse must notify the DSMC via email including the subject ID, date of event, grade, relatedness, expectedness, and a short narrative. DSMC will review data entered into OnCore®.
3. For routine reporting, the events will be reported to IRB as part of the annual continuing progress report and the DSMC will review data entered into OnCore® at the time of scheduled monitoring.
4. Fatal or life-threatening SAEs meeting the criteria indicated in the above table will be reported to FDA no later than seven calendar days after study staff's initial awareness of the event. If the SAE is not fatal or life-threatening and meets the above criteria, the timeline for submitting an IND safety report to FDA is no later than 15 calendar days after study staff's initial awareness of the event. See section 6.2.3 for detailed reporting instructions.

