## 8.5 DSMC

The Medical College of Wisconsin Cancer Center places the highest priority on ensuring the safety of patients participating in clinical trials. Every cancer interventional trial conducted at MCW includes a plan for safety and data monitoring.

More information can be found related to the MCWCC Data and Safety Monitoring Plan at the MCWCC website ([Data and Safety Monitoring Plan](#)).

This study will be reviewed by the Medical College of Wisconsin Cancer Center Data and Safety Monitoring Committee (MCWCC DSMC). A summary of the MCWCC DSMC activities are as follows:

- Review the clinical trial for data integrity and safety
- Review all DSM reports
- Submit a summary of any recommendations related to study conduct
- Terminate the study if deemed unsafe for patients

A copy of the MCWCC Data and Safety Monitoring Plan and membership roster will be maintained in the study research file and updated as membership changes. The committee will review reports from the study PI twice annually (or more frequently if needed) and provide recommendations on trial continuation, suspension, or termination as necessary.

Any available DSMC letters will be submitted to the IRB of record as required.

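### As printed, Table 4 requires no named or expedited DSMC notice for unrelated or unlikely grade 4-5 SAEs, deaths included, although grade 4 events in its AE columns reach the DSMC within 5 calendar days

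*Combined protocol and SAP*

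**What the plan says.** Table 4 in Section 6.2.2 routes events by attribution, seriousness, grade and expectedness. The row for "Unrelated Unlikely" attribution reads as follows:

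- SAEs of grade 1 to 3, expected or unexpected: "IRB 1 and DSMC 2 - Routine Review 3".
- SAEs of grade 4 and 5, expected or unexpected: "IRB 1 - Routine Review 3".
- Grade 3 unexpected events in the AE columns: DSMC, routine review.
- Grade 4 events in the AE columns, expected or unexpected: "DSMC 2 - Within 5 calendar days".

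Footnote 3, attached to every routine cell, explains what routine means. For the IRB, "the events will be reported to IRB as part of the annual continuing progress report". For the DSMC, it means looking at OnCore data when monitoring is scheduled. Footnote 2 describes the e-mail notice to the DSMC and ties it to expedited reporting. Section 6.2.2 also requires every SAE to be documented in OnCore, whatever its attribution. Section 8.5 sets DSMC review of the investigator's reports at twice a year, or more often if needed.

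**The concern.** Within one attribution class, the urgency of the DSMC route should not fall as events become graver. Here a grade 4 event in the AE columns prompts an e-mail within days. A fatal or life-threatening SAE with the same attribution prompts none, and it also loses the DSMC label that milder SAEs carry. The protocol gives no reason for this.

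The attribution that decides the route is the judgement of the investigator or treating physician (Section 6.2.1), in a small study with no control group against which to test it. SAEs are collected from consent until 30 days after the last dose, and dosing runs to the day before surgery, so the window covers the operation and early recovery. The Toxicity text in Section 1.1 acknowledges that earlier trials did not study surgical risk specifically, and a pre-operative coagulation test was added as a safeguard. A severe postoperative bleed could readily be attributed to the operation and classed as unlikely to be related. It would then fall into the cell with no prompt DSMC notice, although Section 8.5 gives that committee the task to "Terminate the study if deemed unsafe for patients" and Section 8.3 classifies the protocol as high risk.

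**Working it through.** The plan states no figure to reproduce. The check is a cell-by-cell reading, a search for any other route to the DSMC, and a simple bound on the delay.

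**Step 1. Do the cells map to the columns?** The header has seven columns: SAE grade 1-3 (expected, unexpected), SAE grade 4-5 (expected, unexpected), AE grade 3 (unexpected) and AE grade 4 (expected, unexpected). The Unrelated/Unlikely row has seven filled cells, so they map one to one.

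| Event, Unrelated/Unlikely row | DSMC named in the cell? | DSMC timing |
|---|---|---|
| SAE grade 1-3 | Yes | Routine |
| SAE grade 4-5 | No | Only through footnote 3: OnCore at scheduled monitoring |
| AE grade 3, unexpected | Yes | Routine |
| AE grade 4 | Yes | 5 calendar days |

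**Step 2. Is the pattern confined to this row?** Yes. In the Possible/Probable/Definite row, an unexpected grade 4-5 SAE is "IRB 1 and DSMC 2 - Within 5 calendar days", and an expected one goes to the DSMC in the same time.

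**Step 3. Does another section supply a prompt DSMC notice?**

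- Section 6.2.3: the IND safety report needs an event that is at least possibly related, unexpected and serious. Unrelated and unlikely events are outside it, and it is addressed to FDA.
- Section 6.5: a DLT must be definitely or probably related. These events do not count towards the early safety rule.
- Section 6.2.2: entry in OnCore is documentation. No notice to the DSMC follows from it.
- Section 8.1: the investigator monitors continuously and sends safety and progress reports to the DSMC, but no clock is attached to a single event.
- Section 8.2: regular review of reportable SAEs is by the study team.
- Section 8.5: DSMC review is twice yearly, or more often if needed.

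None of these restores an expedited notice.

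**Step 4. How long could the delay be?** Inputs: 5 calendar days (Table 4), two DSMC reviews a year (Section 8.5), and eight patients in about one year (Protocol Summary).

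- Longest interval between reviews, if scheduled monitoring is the twice-yearly review and the reviews are evenly spaced: 365 / 2 = 182.5 days, about 6 months.
- Relative to the AE clock: 182.5 / 5 = 36.5 times as long.
- Share of the planned accrual period: 182.5 / 365 = 0.5. With even accrual (also assumed), that is 8 x 0.5 = 4 patients, the size of the first cohort in Section 6.5.

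This is an upper bound under the stated assumptions. An earlier review would shorten it.

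**The case against.** Five arguments go the other way.

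1. *The DSMC is not shut out.* A reader might infer that these SAEs go to the IRB alone, once a year, and never reach the DSMC. The documents do not support that. The cell carries footnote 3, which includes DSMC review of OnCore, and every SAE must be in OnCore. This stands in full: what is missing is a named and prompt notice.

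2. *Other safeguards exist.* Section 4.10 lets the investigator, sponsor or IRB, as well as the DSMC, suspend or terminate the study. The study team reviews reportable SAEs, and an early safety assessment goes to the DSMC after four patients. This also stands. It softens the consequence, but none of these gives the independent committee prompt notice of the event.

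3. *The table may be damaged.* Four of the seven cells in the second row are blank in the text available, which suggests merged cells. In the expected grade 4-5 column, an IRB-only cell sits above a DSMC-only cell, which could be one merged cell split in two. This stands for that column. The unexpected column is firmer, because its second-row entry already names both bodies and leaves no stray DSMC line to move up. A line lost from the cell still cannot be excluded.

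4. *A grade 4 SAE is also a grade 4 AE.* Section 6.2.1 speaks of adverse events as including serious ones, so a grade 4 SAE might trigger the 5-day cell in the AE columns. The reading is arguable, but it would make some of the SAE cells redundant. Even if it is accepted, grade 5 events have no AE column, so deaths would remain without a prompt notice.

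5. *IRB routing lies partly elsewhere.* A reader might also infer from the second row that a related, expected grade 4-5 SAE is never reported to the IRB. That cannot be established. Footnote 1 points to institutional IRB policies that are not in the documents, and that column is the one most likely to be a merged cell. No change is proposed there.

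**Conclusion.** The point holds in a limited form: in the Unrelated/Unlikely row as printed, the gravest SAEs have a slower and less explicit DSMC route than grade 4 events in the AE columns, and no other section makes up the difference. The unexpected grade 4-5 cell is the firm part; the expected one depends on the original layout.

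The contrast between an expedited and a non-expedited notice rests on the printed cells. The figure of about 6 months rests in addition on equating scheduled monitoring with the twice-yearly review, which the documents do not do. This is a weakness in safety oversight that should be corrected. It has no bearing on the PK estimates or the sample size.

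**What to change.** First, compare Table 4 with its original layout, in particular the two grade 4-5 SAE columns and any merged cells. If the row reads as printed, add the DSMC to the unrelated/unlikely grade 4-5 SAE cells, giving priority to the unexpected one, with a clock no slower than the 5 calendar days already set for grade 4 events in the AE columns. It would also help to state whether the AE columns cover only non-serious events, and whether scheduled monitoring in footnote 3 means the twice-yearly review in Section 8.5.

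The cost is an edit to two table cells and a clarifying line, made by amendment, plus a few e-mails to the DSMC in an eight-patient trial. No new data collection is needed, since every SAE is already entered in OnCore.

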### 6.2.3 Reporting Instructions

An IND safety report will be submitted for any adverse event that meets all three definitions: possibly related to the study drug, unexpected, and serious. If the adverse event does not meet one of the above definitions, it should not be submitted as an expedited IND safety report.

Any relevant additional information that pertains to a previously submitted IND safety report will be submitted to FDA as a Follow-up IND Safety Report without delay, as soon as the information is available (21 CFR 312.32(d)(2)).

#### Suggested Reporting Form:

US FDA MedWatch 3500A:

<http://www.fda.gov/Safety/MedWatch/HowToReport/DownloadForms/default.htm>

### 6.3 Unanticipated Problem Involving Risk to Subject or Other (UPIRSO)

The investigator and his or her team will follow the Medical College of Wisconsin policies related to unanticipated problems involving risks to subjects or others. This information may be found on the [Human Research Protection Program website](#).

### 6.4 Subject Complaints

If a complaint is received by anyone on the study staff, it will be discussed with the study staff and will be addressed on a case-by-case basis. The PI will be notified of any complaints. Complaints will be reported to the IRB if indicated.

If the subject has questions about his or her rights as a study subject, wants to report any problems or complaints, obtain information about the study or offer input, the subject can call the Medical College of Wisconsin/Froedtert Hospital research subject advocate at [contact]. This information is provided to the subject in their consent.

A product complaint is a verbal, written or electronic expression that implies dissatisfaction regarding the identity, strength, purity, quality or stability of a drug product. Individuals who identify a potential product complaint situation should immediately contact the drug manufacturer and report the event. Whenever possible, the associated product should be maintained in accordance with the label instructions pending further guidance from a drug manufacturer representative. Product complaints in and of themselves are not reportable events. If a product complaint results in an SAE, an SAE form should be completed.

### 6.5 Safety Assessment

Dose-limiting toxicity (DLT) is defined as the occurrence of any grade  $\geq 3$  adverse event (AE) that is definitely or probably related to ATB and occurs during the study.

An early safety assessment will be performed after the first four patients complete protocol therapy and reported to the DSMC. In the event of 0-1 DLT events, the experimental therapy is considered safe and the study will proceed to the second cohort of four patients. In the event of  $\geq 2$  DLTs in the first four patients, the study chairs and DSMC will recommend proceeding with the second cohort at dose level -1 or dose level -2.

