## **4.6 Discontinuation of Study Treatment, Withdrawal, and Compliance**

Discontinuation from the study treatment does not mean discontinuation from the study. Subject will be considered in follow-up, study procedures should still be completed as indicated by the study protocol, and AEs/SAEs will continue to be reported according to this protocol.

In the absence of treatment delays due to adverse events, study treatment/intervention may continue until:

- Disease progression.
- General or specific changes in the subject's condition renders the subject unacceptable for further treatment in the investigator's judgment.
- Inter-current illness that prevents further treatment administration.
- Subject decides to withdraw from the study.
- The subject has significant noncompliance with the protocol (see below).
- Unacceptable adverse event(s) and/or dose level reduction beyond requirements as detailed in this protocol.
- Study stopping rules are met.

Subjects who sign the informed consent form, enroll and receive the study intervention, but subsequently withdraw, or are withdrawn or discontinued from the study will not be replaced.

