#### **4.9 End of Study Definition**

A participant is considered to have completed the study if he or she completed all phases of the study, including the last visit or the last scheduled procedure shown in the calendar of events or has been discontinued.

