### 5.7 Dose Modifications

As indicated in the study calendar, a complete metabolic panel (including LFTs) will be performed mid-way during the course of ATB. Adverse events will be graded according to CTCAE v.5.

Adverse Event (CTCAE, v. 5)	Action
Non-hematological, grade 1 or 2	Continue ATB therapy at full dose prescribed. Apply maximum supportive care recommendations. If persistent duration of grade 2 adverse event is affecting quality of life, a one-time decrease of 25%.
Non-hematological, grade 3 or 4	
Apply maximum supportive care recommendations. Hold ATB therapy until recovery to grade <math>\leq 1</math> (up to 7 days).
 
If concomitant elevation of AST/ALT 3 times the upper limit of normal and bilirubin elevation 2 times the upper limit of normal (Hy's Law criteria) the patient must be removed from study treatment, ATB must be permanently discontinued.
 
If recurrence of adverse event after drug hold and/or interruptions is observed and maximum supportive care measures applied, a dose reduction by 25% is recommended. ATB should not be used at doses below 50%

Non-hematological, grade 3 or 4 and adverse events NOT resolved to grade $\leq 2$ within a maximum of 14 calendar days from last planned administration	Dose reductions by 25% (up to 2 reductions) will be considered after maximum supportive care recommendations are introduced.

Dose Level	Dose
-2	600 mg TID
-1	900 mg TID
0	1200 mg TID

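### A permanent stop under the 5.7 liver rule is not a DLT in 6.5 if rated possibly related or graded below 3, so two in the first four patients could still be labelled safe at full dose

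*Combined protocol and SAP*

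**What the plan says.** Section 6.5 (Safety Assessment) sets two conditions for a DLT: grade 3 or higher, and an event "that is definitely or probably related to ATB and occurs during the study". It then fixes one look: "An early safety assessment will be performed after the first four patients complete protocol therapy and reported to the DSMC". With 0 or 1 DLT, "the experimental therapy is considered safe and the study will proceed to the second cohort of four patients". With two or more, the study chairs and DSMC recommend dose level -1 (900 mg three times daily) or -2 (600 mg three times daily) for the second cohort.

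Section 5.7 (Dose Modifications) has a separate liver rule. If AST/ALT at 3 times ULN coincides with bilirubin at 2 times ULN, "the patient must be removed from study treatment, ATB must be permanently discontinued". The rule carries no attribution condition. It sits in the table row for grade 3 or 4 non-hematological events, but its trigger is written in multiples of ULN, not as a grade.

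Section 6.1.3 makes possibly related a category of its own, below probably and definitely related, and describes it thus: "There is some evidence to suggest a causal relationship".

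**The concern.** The event that the protocol treats as serious enough to end a patient's treatment for good is not automatically an event that its dose rule counts. The 6.5 look is the only numerical rule for the second cohort's dose. On its wording, it can give the safe result at full dose after two of four patients had to stop ATB for liver toxicity that may be drug-related. Four more patients would then start at the same dose.

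Possibly related is a plausible rating here. Under 6.1.3, probably related requires that the influence of other factors be unlikely. Yet 5.8 does not restrict concomitant medication in general, and the inclusion criteria admit AST or ALT up to 3 times ULN and bilirubin just under 2 times ULN. Competing explanations for a liver event may therefore be available.

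Elsewhere the protocol treats possible as related. Table 4 groups it with probable and definite, and 6.2.3 accepts it for an IND safety report.

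**Working it through.** **Step 1: apply the rule as written.** The outcome for two liver-rule stops in the first four patients, with no other DLT, is:

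| Grade of both | Attribution of both | DLTs under 6.5 | 6.5 result |
|---|---|---|---|
| 3 or higher | probable or definite | 2 | lower dose |
| 3 or higher | possible | 0 | safe, full dose |
| below 3 | possible | 0 | safe, full dose |
| below 3 | probable or definite | 0 | safe, full dose |

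Adding possible to the DLT definition would repair the second row only. Naming the 5.7 stop itself as a DLT repairs the last three.

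**Step 2: how likely is it?** The documents give no liver-stop rate and no operating characteristics for 6.5, so there is no stated figure to reproduce and every rate below is an assumption. Let p be the chance that a patient has a liver stop rated possible or higher, and q the share of those rated possibly related. Take all as grade 3 or higher, with n = 4.

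P(X ≥ 2; p) = 1 − (1−p)^4 − 4p(1−p)^3.

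Counted stops have rate p(1−q), so the chance of at least two stops with fewer than two counted is P(X ≥ 2; p) − P(X ≥ 2; p(1−q)). For p = 0.05 and q = 0.5 this is 0.0140 − 0.0036 = 0.0104.

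| | p = 1% | p = 5% | p = 10% |
|---|---|---|---|
| q = 0.25 | 0.03% | 0.6% | 2.2% |
| q = 0.5 | 0.04% | 1.0% | 3.8% |
| q = 0.75 | 0.06% | 1.3% | 4.9% |
| none counted (all possible, or all below grade 3) | 0.06% | 1.4% | 5.2% |

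The last row is P(X ≥ 2; p) itself and is the ceiling. The narrower case of at least two stops with none counted, at q = 0.5, is the sum over k = 2 to 4 of P(X = k) × 0.5^k: 0.01%, 0.3% and 1.3%.

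**Step 3: the single-stop case.** P(X = 1) = 4p(1−p)^3 gives 3.9%, 17.1% and 29.2%. If no other DLT occurs, one stop falls in the 0–1 band whether or not it is counted.

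**Step 4: cost of counting more events.** Suppose 2% to 5% of patients had a liver event not caused by ATB that met the 5.7 criterion and was rated possible. The chance of two or more in four is then 0.2% (p = 0.02: 0.0023) to 1.4% (p = 0.05: 0.0140).

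De-escalation would leave at most four patients at 1,200 mg. Section 7.1 assumes an SD of 50% of the mean. Its planned margin reproduces: 0.5 × 2.571 / √6 = 0.525. With four patients it is 0.5 × 3.182 / √4 = 0.796, about ±80% of the mean.

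The model leaves out one liver stop combined with a different DLT, so both the missed and the false-trigger figures are partial.

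**The case against.** Limiting DLTs to definite and probable events is a legitimate choice for specificity in an eight-patient study with 7 to 28 days of dosing. Section 5.7 protects the individual and 6.5 sets a cohort dose, so different thresholds need not conflict. That stands, and the point does not dispute the attribution threshold for other adverse events.

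The scenario is also remote. Section 1.1 reports no liver effect in a study with 300 participants on ATB and only a few cases of jaundice in the largest study, and active liver disease is an exclusion. That stands too, and it limits the weight of the point.

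A reader might infer that the second cohort would start at full dose with nobody looking. The documents do not support this. Table 4 sends unexpected serious events rated possible or higher to the IRB and DSMC "Within 5 calendar days", and two liver stops in four patients would probably be unexpected in frequency under 6.1.4. Section 6.2.3 requires an FDA report for a serious, unexpected, possibly related event. Section 4.10 allows suspension, 8.2 has the team address the intervention for the next subject, and 8.5 lets the DSMC terminate. For events of grade 3 or below, the five-day route depends on the event being classed as serious and unexpected. None of these provisions alters the 6.5 count or label. Section 6.5 does not confine its report to a DLT tally, but it does not ask for liver stops either.

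A reader might also infer that a permanently stopped patient falls outside the first four because protocol therapy was not completed. Sections 4.6 ("Discontinuation from the study treatment does not mean discontinuation from the study") and 4.9 (a participant has completed the study after the last procedure "shown in the calendar of events or has been discontinued") largely settle this in favour of inclusion. Either way, the events described are not DLTs.

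Finally, the liver rule's place in the grade 3 or 4 row could mean that it applies only at those grades. If so, the below-grade-3 route closes and the attribution route remains.

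**Conclusion.** The gap is real on the text and needs no assumed figure: a liver-rule stop rated possibly related, or graded below 3, is not a DLT, and two of them leave 6.5 at zero. Its likely effect is small. Across the assumed rates of 1% to 10%, the chance that the rule misses two or more stops runs from 0.03% to 5.2%, and prior safety reports point to the low end. These figures rest on the assumed rates, on independent patients, and on p covering only stops rated possible or higher.

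This is a cheap improvement worth considering. It does not show that the safety plan as a whole fails or that the general DLT definition is wrong.

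**What to change.** Two changes to 6.5:

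- Count any permanent discontinuation under the 5.7 liver criterion as a DLT, at any CTCAE grade, unless it is rated unlikely or unrelated. Leave the definition for all other events as it is.
- Require the four-patient DSMC report to list every liver-rule stop and every grade 3 or higher event rated possible or higher, including when the DLT count is 0 or 1.

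The first change closes the two-stop gap. The second also covers the likelier single-stop case, which the first leaves in the 0–1 band, and it costs no PK precision. If only one is adopted, the listing is the easier to accept.

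The cost is about two sentences and one listing. The downside of the first change is the false trigger worked out above (0.2% to 1.4% at assumed rates of 2% to 5%). If it occurred, the estimate at 1,200 mg would rest on at most four patients, with a margin of about ±80% of the mean instead of ±52.5%.
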